### **Exploratory Statistical Aim 1: To validate TAPS tool using WHO ASSIST as gold standard.**

The TAPS tool is rapidly becoming recognized as a high quality substance use screener for outpatient health care settings. Given the somewhat limited opioid using sample in the main outcomes study ( $\leq 5\%$  for prescription opioids;  $< 4\%$  for heroin\*), the current study offers an important opportunity to further validate this instrument in a novel outpatient setting, community pharmacy, among a large opioid using population.

The performance of TAPS Tool will be evaluated relative to WHO ASSIST. We plan to compare subjects' responses to each substance of TAPS Tool with their responses to the corresponding domains of WHO ASSIST. The TAPS tool has four domains, and WHO ASSIST has 9 domains. Domains on the ASSIST will be combined with those of the TAPS Tool, see **Table 4** for details:

**Table 4: combinations of substances for WHO ASSIST**

ASSIST (past 3 months)	TAPS 1 (past 12 months)			
	Tobacco	Alcohol	Illicit Drug	Prescribed Medication
Tobacco products (cigarettes, chewing tobacco, cigars, etc.)	X			
Alcoholic beverages (beer, wine, liquor, etc.)		X		
Cannabis (marijuana, pot, weed, hash, etc.)			X	
Cocaine (coke, crack, etc.)			X	
Amphetamine type stimulants (speed, diet pills, ecstasy, methamphetamine, crystal-meth, etc.)			X	X
Inhalants (nitrous, glue, poppers, etc.)			X	
Sedatives or sleeping pills (Valium, Rohypnol, Ativan, Xanax, Klonopin, GHB, etc.)				X
Hallucinogens (LSD, acid, mushrooms, PCP, Special K, etc.)			X	
Opioids (heroin, morphine, methadone, codeine, buprenorphine, suboxone, Oxycontin, Percocet, Vicodin, etc.)			X	X
Other (K2, Spice, Synthetic spice, Synthetic marijuana)			X	

The level of agreement between TAPS tool with the established risk levels of low, moderate and high on the WHO ASSIST will be evaluated with similar methods as described in Aim 2: ROC analysis will be used to examine concordance between each domain of the TAPS Tool and the corresponding clustered domain of WHO ASSIST. Risk levels of the WHO ASSIST for each clustered domain are defined as follow:

- WHO ASSIST Tobacco Domain:
  - Moderate and High risk  $>3$
  - Low risk  $\leq 3$
- WHO ASSIST Alcohol Domain:
  - Moderate and High risk  $>10$
  - Low risk  $\leq 10$

- WHO ASSIST Illicit Drug Domain:
  - Moderate and High risk  $>3$
  - Low risk  $\leq 3$
- WHO ASSIST Prescribed Medication Domain:
  - Moderate and High risk  $>3$
  - Low risk  $\leq 3$ .

For each of these binary risk categories, Area under the ROC curve (AUC) values will be used to determine the overall discriminating ability of TAPS tool on each of the 4 domains.

The confusion table will be provided (see **Table 5 example of alcohol domain Confusion Table**) and the following statistical measurements of agreement, all with their respective 95% confidence intervals will be provided: Spearman correlation coefficient, Goodman and Kruskal's Gamma, and Kendall rank correlation coefficient. A logistic regression model will be built to estimate the magnitude of association between the metrics, while controlling for other relevant risk factors.

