7.2.2 WHO ASSIST

The WHO ASSIST will be used as the gold standard to which the NS metric will be compared. The WHO ASSIST was constructed in a large-scale multi-country study, which demonstrated criterion, construct, concurrent, discriminant validity.² This assessment contains between 8-74 Likert scale items, depending on the number of substances endorsed by study participants, and will require 5-15 minutes to complete. The WHO ASSIST asks about use of the following

substances in the past 3 months and lifetime: tobacco, alcohol, cannabis, cocaine, amphetamine, inhalants, sedatives, hallucinogens, opioids, and other drugs.

In addition to the WHO ASSIST, we will capture 2 additional opioid items from an adapted WHO ASSIST, developed by McNeely, et al.⁵³ In this adapted version, opioid items specifically inquire about use of prescription opioids and heroin. These items have been tested in an audio assisted computerized format and have demonstrated reliability.⁵³ These items will *not* be used in our a priori assessment of the NS score and the WHO ASSIST.

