7.2.3 TAPS Tool

Substance use will also be captured using TAPS 1/2 tool, which has demonstrated concurrent validity.¹ This assessment contains between 5-14 items regarding a respondent's substance use in the last 3 and 12 months. It specifically addresses use of tobacco and alcohol as well as illicit and prescription drug misuse. This assessment will require 5-15 minutes to complete. This measure will be captured to provide additional information regarding its psychometric properties compared to the WHO ASSIST.

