### **2.2.3 TAPS**

The TAPS Tool consists of a 5-item screening for tobacco use, unhealthy alcohol use, prescription medication misuse, and illicit substance use. Positive reports on the screener result in respondents subsequently being asked 9 additional substance specific items. Scoring on the TAPS Tool involves summing respondents' answers to the substance specific questions, resulting in a 0-3 ordinal score for each drug (0=No use in the past 3 months; 1= problem use; 2= higher risk). The TAPS Tool has demonstrated concurrent validity. This measure will be captured in order to provide additional information regarding its psychometric properties compared to the WHO ASSIST.

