**Table 5. Confusion matrix for Alcohol Domain**

Predicted risk levels defined by WHO ASSIST		TAPS Tool observation				
		0	1	2	3	4
Low risk level	XX (XX.XX%)	XX (XX.XX%)	XX (XX.XX%)	XX (XX.XX%)	XX (XX.XX%)	XX (XX.XX%)
High/moderate risk level	XX (XX.XX%)	XX (XX.XX%)	XX (XX.XX%)	XX (XX.XX%)	XX (XX.XX%)	XX (XX.XX%)

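### SAP Table 4 sets the TAPS validation as a 12-month TAPS-1 screen against 3-month ASSIST domains, in conflict with the 3-month TAPS score in SAP 2.2.3 and the levels in Table 5

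*SAP*

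**What the plan says.** Protocol 5.2 makes further validation of the TAPS Tool against the WHO ASSIST the secondary objective. Protocol 9.1.1 and 9.3 leave the details to the SAP, where the work is Exploratory Statistical Aim 1. That text sends the reader to Table 4 for how ASSIST and TAPS domains are matched. The table's rows are ASSIST substances under the heading "ASSIST (past 3 months". Its columns are Tobacco, Alcohol, Illicit Drug and Prescribed Medication under the heading "TAPS 1 (past 12 months". The AUC is then to be computed for TAPS on each of four domains, and the output shells in Appendix 1 list the same four.

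SAP 2.2.3 describes a different quantity: "Scoring on the TAPS Tool involves summing respondents' answers to the substance specific questions". The score is given for each drug on a 0 to 3 range, with the labels "0=No use in the past 3 months; 1= problem use; 2= higher risk". Table 5, the example confusion table for alcohol, has columns 0 to 4 under "TAPS Tool observation".

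The protocol says that TAPS asks "regarding a respondent's substance use in the last 3 and 12 months" (7.2.3) and that the ASSIST asks about "substances in the past 3 months and lifetime: tobacco, alcohol" and the other listed substances (7.2.2).

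**The concern.** A validation against a reference standard should compare like with like. Read plainly, Table 4 makes the 12-month screen the index test and a measure headed as 3-month the reference. A patient whose only use was 4 to 12 months ago can then rank as exposed on TAPS and low risk on the ASSIST. Such disagreement reflects the length of the recall window and not how well TAPS detects risk, yet it would be reported as TAPS performance.

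Section 2.2.3 points to a score without this problem, but the SAP does not say that this score is the one analysed. It also gives no rule for turning per-drug scores into the Illicit Drug and Prescribed Medication domains. As the plan stands, the analyst would have to choose the variable, its window and its range after the data are in. At stake are the AUC and agreement results for the protocol's secondary objective.

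**Working it through.** The documents state no power, AUC, sensitivity or specificity for the TAPS aim, so there is no planned figure to reproduce. The check is a comparison of the sections, followed by a bound on the effect.

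**Step 1. The three descriptions of the TAPS variable**

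| Place in SAP | Unit | Window | Levels |
|---|---|---|---|
| Table 4 | four domains | 12 months (TAPS-1) | not stated |
| Section 2.2.3 | each drug | 0 means no use in 3 months | 0 to 3, with only 0, 1 and 2 labelled |
| Table 5 (alcohol example) | one domain | not stated | 0 to 4 |

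No two rows agree throughout, and no text says which one governs.

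**Step 2. A patient whose only use was 4 to 12 months ago**

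- On a TAPS-1 any-use answer over 12 months, the patient is positive.
- On the 2.2.3 score, the patient goes on to the substance-specific items and scores 0.
- On the ASSIST reference, the patient is low risk if the domain score is at most 3 (at most 10 for alcohol). The ASSIST also asks about lifetime use, so low risk is possible but not certain.

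**Step 3. Bound on the specificity loss**

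Let p be the share of ASSIST-low patients in a domain whose only use was 4 to 12 months ago. Moving from the 3-month score to 12-month any-use adds false positives only from this group, at most p per ASSIST-low patient:

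SP(12 months) ≥ SP(3 months) − p

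**Step 4. Bound on the AUC loss**

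For a binary marker, AUC = (SE + SP)/2, so the loss through specificity is at most p/2. Let r be the share of ASSIST moderate- or high-risk patients who are positive on the 12-month answer but score 0 on the 3-month score. Sensitivity then rises by r, and at the bound the net change in AUC is (r − p)/2. The documents give neither p nor r.

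**Step 5. Illustration**

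Assume SE 0.80 and SP 0.90 with matched 3-month windows, so AUC = (0.80 + 0.90)/2 = 0.85, and take r = 0.

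| Assumed p | Lowest SP, any-use in 12 months | Lowest binary AUC | SP, 3-month score | AUC, 3-month score |
|---|---|---|---|---|
| 1% | 0.90 − 0.01 = 0.89 | (0.80 + 0.89)/2 = 0.845 | 0.90 | 0.85 |
| 3% | 0.90 − 0.03 = 0.87 | (0.80 + 0.87)/2 = 0.835 | 0.90 | 0.85 |
| 5% | 0.90 − 0.05 = 0.85 | (0.80 + 0.85)/2 = 0.825 | 0.90 | 0.85 |
| 10% | 0.90 − 0.10 = 0.80 | (0.80 + 0.80)/2 = 0.80 | 0.90 | 0.85 |

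Every value in this table rests on assumed inputs. It shows scale and is not a forecast.

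**The case against.** The best defence is that Table 4 only groups substances. Its title speaks of combinations, no sentence names the 12-month answer as index test, and the only TAPS score the SAP defines gives 0 to a patient with no use in the last three months. On that reading there is no window mismatch and no loss. The ASSIST reference is a score cut-off from an instrument that also covers lifetime use, so a patient who stopped recently need not be low risk. Exploratory Aim 1 sets no TAPS cut-off, so specificity is not a planned output there. Table 5 is a single example whose layout may have suffered in conversion, and its range says nothing about recall. Both documents call the analysis exploratory.

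Much of this stands. A reader might infer from Table 4 that everyone who stopped 4 to 12 months ago is bound to count as a TAPS false positive. The documents do not support that, for the reasons just given. The specificity figures apply only if an any-use cut is used, and the net AUC effect also depends on any gain in sensitivity.

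The defence does not settle which variable is analysed. The 2.2.3 score is per drug and the ROC is per domain. Without a combination rule, that score cannot enter the Illicit Drug or Prescribed Medication analysis as written. The four domains analysed are exactly the columns that Table 4 heads as TAPS-1 over 12 months, so the plain reading still leads to the 12-month screen.

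**Conclusion.** The point holds as a conflict over the index test. Table 4, section 2.2.3 and Table 5 describe three different TAPS variables, and following Table 4 mixes a difference in recall window into the TAPS AUC and agreement results. The size runs from zero, if the 2.2.3 score is used, to a specificity loss of at most p and a binary AUC loss of at most p/2, if a 12-month any-use answer is used. The bound takes an any-use cut, and p must be assumed. The direction is downward through specificity; a partly offsetting gain in sensitivity cannot be excluded.

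This does not show that TAPS performance will be understated by any particular amount. It affects the protocol's secondary objective, which the SAP analyses as exploratory. The primary NS metric analyses do not depend on it.

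**What to change.** Before database lock, amend the SAP as follows:

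- Name the 3-month substance-specific TAPS score of section 2.2.3 as the index test for the ROC, confusion-table and correlation analyses of Exploratory Aim 1.
- State how per-drug scores are combined into the Illicit Drug and Prescribed Medication domains, for example as the maximum across the drugs in the domain, and list which drugs feed each.
- Give the score's range and the label of every level, state any cut-off, and align Tables 4 and 5 and section 2.2.3 to it.
- Use the same definition for the TAPS prescribed medication domain in Exploratory Aim 2.
- Report the 12-month TAPS-1 screen against the ASSIST as a separate secondary row in each domain, with the difference in window noted.

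The cost is a few table edits, one written combination rule and one extra row per domain. No new data are needed, since protocol 7.2.3 already has TAPS answers collected for both 3 and 12 months.

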**Table 1. Study Measures**

Domain	Name	No. of Items	Min. to Complete
Opioid use severity	WHO Alcohol, Smoking and Substance Involvement Screening Test (ASSIST): Opioid Items 	8	≤5
	WHO Alcohol, Smoking and Substance Involvement Screening Test (ASSIST): Adapted heroin and prescription opioid items 3*	16	≤5
	Tobacco, Alcohol, Prescription Medication, and Other Substance Use (TAPS) 1 / 2 Tool: Prescription drug and prescription opioid items 	2-4	≤1
	Tobacco, Alcohol, Prescription Medication, and Other Substance Use (TAPS) 1 / 2 Tool: Illicit drug and heroin items 	2-4	≤1
Opioid medication misuse	Prescription Opioid Misuse Index 	6	≤5
Opioid overdose	Overdose Experiences, Self and Witnessed—Drug (OESWD) 	1	≤1
Non-opioid drug use severity	WHO Alcohol, Smoking and Substance Involvement Screening Test (ASSIST): Non-opioid drug use items 	8-72	5-15
	Tobacco, Alcohol, Prescription Medication, and Other Substance Use (TAPS) 1 / 2 Tool: Non-opioid items 	12-25	≤5
Depression	Patient Health Questionnaire-2 	2	≤1
Physical Health	Short Form-12: General health subscale 	1	≤1
	Brief Pain Inventory 	8	≤5
Demographics	PhenX demographics: age, education, gender, race, ethnicity, health insurance, employment, marital status	10	<5
		Totals: 76-157	40-50

\* The adapted heroin and prescription opioid items will not be employed in the a priori analyses.

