**Exploratory Statistical Aim 2: To assess the association between the NS metric and other measurements of opioid misuse.**

In this exploratory aim, we will assess the relationship between the NS metric with the established risk levels of low, moderate and high risk and 1) ordinal prescription and heroin use scores from the TAPS Tool (prescribed medication and heroin domains), 2) a positive misuse indication from (POMI), and 3) overdose frequency history.

Risk levels will be defined as follow:

- TAPS Tool prescribed medication domain:
  - High risk  $\geq 2$ ;
  - Low risk  $< 2$ .

- POMI:
  - High risk  $\geq 2$ ;
  - Low risk  $< 2$ .
- Overdose Frequency History - OESWD domain:
  - Any Overdose  $> 0$ ;
  - No Overdose = 0.

We will likewise employ the above described statistical analyses for Exploratory Aim 1 and assess the association and agreement level between NS metric and the TAPS Tool, POMI, and Overdose Frequency History with the:

- Confusion table;
- AUC of ROC analysis;
- Spearman Correlation Coefficient;
- Goodman and Kruskal's Gamma;
- Kendall rank correlation coefficient;
- Ordinal Logit Regression.

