Results for Exploratory Aim 1	Table 5.1	CP	TAPS Tool ROC curve for discriminating high risk vs low risk groups defined by WHO ASSIST, by domains (Tobacco, Alcohol, Illicit Drug, Prescribed Medication)
	Table 5.2	CP	TAPS Tool ROC curve for discriminating high risk vs low risk groups defined by WHO ASSIST, by domains (Tobacco, Alcohol, Illicit Drug, Prescribed Medication), by gender
	Table 5.3	CP	Summary of AUC of ROC curve for each domain
	Table 5.4	CP	Summary of AUC of ROC curve for each domain by gender
	Table 5.5	CP	Confusion Table for TAP Tool vs WHO ASSIST, for each domain
	Table 5.6	CP	Confusion Table for TAP Tool vs WHO ASSIST, for each domain, by gender
	Table 5.7	CP	Summary of Kappa Coefficient and Correlation Analysis Results, WHO ASSIST vs TAP Tools for each domain
	Table 5.8	CP	Summary of Kappa Coefficient and Correlation Analysis Results, WHO ASSIST vs TAP Tools for each domain, by gender
	Table 5.9	CP	Summary of ordinal logit regression results for each domain
	Table 5.10	CP	Summary of ordinal logit regression results for

Section	Table/Figure #	Analysis Population	Title
Results for Exploratory Aim 2 – explore association between NS metric vs TAP Tools			each domain, by gender
	Table 6.1.1	CP	Confusion Table for NS metric with established cut-off threshold vs TAPS Prescribed Medication Domain
	Table 6.1.2	CP	Confusion Table for NS metric with established cut-off threshold vs TAPS Prescribed Medication Domain, by gender
	Figure 6.1.3	CP	NS metric ROC curve for discriminating high risk vs low risk opioid misuse patients (defined by TAPS)
	Figure 6.1.4	CP	NS metric ROC curve for discriminating high risk vs low risk opioid misuse patients (defined by TAPS), by gender
	Table 6.1.5	CP	Summary of AUC of ROC curve, for NS metric vs TAPS
	Table 6.1.6	CP	Summary of AUC of ROC curve, for NS metric vs TAPS by gender
	Table 6.1.7	CP	Summary of Kappa Coefficient and Correlation Analysis Results, NS metric vs TAP Tools
	Table 6.1.8	CP	Summary of Kappa Coefficient and Correlation Analysis Results, NS metric vs TAP Tools, by gender
	Table 6.1.9	CP	Summary of ordinal logit regression results, NS metric vs TAP Tools
Results for Exploratory Aim 2 – explore association between NS metric vs POMI Tools	Table 6.2.1	CP	Confusion Table for NS metric with established cut-off threshold vs POMI
	Table 6.2.2	CP	Confusion Table for NS metric with established cut-off threshold vs POMI, by gender

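### The TAPS validation counts the combined ASSIST opioid item in both the illicit-drug and the prescribed-medication reference, and plans no heroin or prescription-opioid TAPS result

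*SAP*

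**What the plan says.** SAP 3.5, Exploratory Statistical Aim 1, validates TAPS against ASSIST. Its rationale is that the earlier TAPS study held few prescription-opioid and heroin users. It undertakes to compare "responses to each substance of TAPS Tool with their responses to the corresponding domains of WHO ASSIST", then works with four pooled domains. Table 4 assigns ASSIST substances to those domains. The row "Opioids (heroin, morphine, methadone, codeine, buprenorphine, suboxone, Oxycontin, Percocet, Vicodin, etc" carries a mark under both Illicit Drug and Prescribed Medication, as does the row "Amphetamine type stimulants (speed, diet pills, ecstasy, methamphetamine, crystal-meth, etc". Both domains use the same reference cut: above 3 is moderate or high risk. No rule is given for combining substance scores into a domain score.

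The Exploratory Aim 1 shells in Appendix 1 (Tables 5.1 to 5.10) follow the same structure, "by domains (Tobacco, Alcohol, Illicit Drug, Prescribed Medication". Exploratory Aim 2 uses "ordinal prescription and heroin use scores from the TAPS Tool (prescribed medication and heroin domains", but only in relation to the NS metric.

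SAP Table 1 keeps the TAPS prescription-opioid items apart from the "Illicit drug and heroin items". It also lists adapted ASSIST items that separate heroin from prescription opioids, with the footnote "The adapted heroin and prescription opioid items will not be employed in the a priori analyses". No exploratory analysis names them either.

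**The concern.** There are two linked problems.

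The first is a contaminated reference. TAPS can tell a prescription-opioid user from a heroin user; the combined ASSIST row cannot. Marking that row in both domains makes a person whose only involvement is with prescription opioids positive on the illicit-drug reference. If TAPS correctly reports no illicit use, the analysis counts a false negative. Heroin-only users produce the mirror error in the prescribed-medication domain. Eligibility requires a dispensed opioid (Protocol 6.3.2.1), so prescription-only positives are to be expected.

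The second is a missing result. Prescription opioids are pooled with sedatives and stimulants, and heroin with cannabis, cocaine and others. The listed outputs would not show how TAPS performs for opioids, which is why the aim exists. TAPS validation is the protocol's secondary objective (Protocol 5.2), so a reader could take a mapping artefact for a weakness of the instrument and find no opioid-specific figure to set against it.

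**Working it through.** **Reading the passages together**

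- TAPS structure (SAP Table 1): heroin sits with illicit drugs, prescription opioids with prescription drugs.
- ASSIST structure (SAP Table 4): one opioid row, marked in both domains.
- Cut (SAP Exploratory Aim 1): above 3 in both domains.
- Combination rule: not stated. Under a sum, a maximum or an any-positive rule, an opioid score above 3 is enough by itself to make the whole domain positive.
- Outputs: AUC for each of the four domains, plus confusion tables, rank correlations and logistic regression on the same domains. None is specific to heroin or prescription opioids.

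**Illustration of size**

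The plan gives no figure to reproduce here. Its 17.1% moderate/high prevalence refers to a 0.5 cut on the opioid domain, not to the cut of 3, so it cannot be used. All inputs below are assumptions:

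- any-positive rule;
- true TAPS illicit sensitivity 0.80;
- I = share truly illicit-positive, 0.05 to 0.15;
- R = share positive through prescription opioids only, 0.03 to 0.14;
- f = TAPS illicit endorsement among everyone not truly illicit-positive, 0.02 or 0.05.

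Apparent sensitivity = (0.80 × I + f × R) / (I + R). For a yes/no TAPS result, AUC = (sensitivity + 1 − f) / 2.

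Without contamination, AUC = (0.80 + 0.98)/2 = 0.89 at f = 0.02, or (0.80 + 0.95)/2 = 0.875 at f = 0.05.

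| I | R | Sensitivity, f = 0.02 | Sensitivity, f = 0.05 | AUC |
|---|---|---|---|---|
| 0.05 | 0.14 | 0.0428/0.19 = 0.225 | 0.0470/0.19 = 0.247 | 0.60 |
| 0.05 | 0.03 | 0.0406/0.08 = 0.51 | 0.0415/0.08 = 0.52 | 0.73–0.74 |
| 0.10 | 0.06 | 0.0812/0.16 = 0.51 | 0.0830/0.16 = 0.52 | 0.73–0.74 |
| 0.15 | 0.03 | 0.1206/0.18 = 0.670 | 0.1215/0.18 = 0.675 | 0.81–0.83 |

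A simulation of 2 million people at f = 0.05 gave sensitivity and AUC of 0.247 and 0.599, 0.519 and 0.735, and 0.674 and 0.812 for the first, second and fourth rows.

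On the SAP's own AUC scale, an instrument that is good without contamination would be rated poor in the first row, fair in the middle two, and still good in the last.

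**Precision of a heroin comparison**

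If 1–4% of 1,523 (15 to 61 people) are heroin-positive and sensitivity is near 0.80, the Wilson 95% interval is 0.55–0.93 for 12/15 and 0.69–0.88 for 49/61.

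**The case against.** The standard ASSIST has one opioid item. Marking it once would drop either heroin from the illicit reference or prescription opioids from the prescribed one, so no clean mapping exists within that instrument. Amphetamines are treated the same way, which suggests a deliberate convention. This stands: the double mark may be intended, although the SAP does not explain it. It is a reason to keep the current mapping in the report, not to rely on it alone when items that separate the two are collected.

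The magnitude rests entirely on assumptions, and this also stands. Prescription-only positives may endorse illicit use more often than other negatives. If 30% of them do, with 2% elsewhere, I = 0.05 and R = 0.14, sensitivity is (0.040 + 0.042)/0.19 = 0.43 and AUC about 0.71. Counting those people as negatives gives a false-positive rate of (0.042 + 0.81 × 0.02)/0.95 = 0.061 and an AUC of 0.87. The loss is then about 0.16, not 0.29; the direction is unchanged and the values stay inside the ranges above. TAPS scores are also ordinal, so the yes/no AUC illustrates the effect and does not predict the planned statistic.

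On the missing outputs, the text does promise a comparison by substance, and Appendix 1 calls its list proposed. But no substance-level method or shell follows. Comparing the TAPS heroin score with the standard combined opioid domain would be simpler, but it would again count prescription-only positives as misses.

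**Conclusion.** The concern holds. Following Table 4 under a sum, maximum or any-positive rule pulls the apparent TAPS illicit-drug sensitivity and AUC downward for a reason unrelated to TAPS. The planned outputs omit the opioid results that motivate the aim.

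The true size is unknown: it depends on the unstated clustering rule and on prevalences at the cut of 3 that the documents do not give. Across the assumed inputs, the AUC loss for a yes/no result runs from about 0.06 (0.875 − 0.8125 or 0.89 − 0.825) to about 0.29 (0.89 − 0.60).

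This should be corrected, but it does not threaten the study. The SAP labels the aim exploratory, and no NS metric cut-point, primary analysis or sample-size argument depends on it.

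**What to change.** 1. Add two comparisons to Exploratory Aim 1 and its shells, each with AUC, sensitivity, specificity and 95% confidence intervals: TAPS heroin score against adapted-ASSIST heroin, and TAPS prescription-opioid score against adapted-ASSIST prescription opioids. Pre-specify the cut on the adapted items, for example the above-3 cut already used for the drug domains, and label the heroin result as low precision.
2. Report the Illicit Drug and Prescribed Medication domains with the opioid row split by the adapted items (heroin to Illicit only, prescription opioids to Prescribed only), next to the current Table 4 mapping, so that the effect of double counting is visible.
3. State how substance scores form a domain score.
4. Settle what the adapted items are. Protocol 7.2.2 says "we will capture 2 additional opioid items from an adapted WHO ASSIST", while SAP Table 1 lists 16. Sixteen would fit two sets of the 8 standard opioid items, but neither document says so. If only two single items are held, no score above 3 can be formed and a yes/no reference must be pre-specified.
5. Name the amphetamine double mark as a remaining limitation.

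The cost is SAP wording and a few tables, with no new data collection, since the SAP footnote bars the adapted items from the a priori analyses only. The downsides are a reference for which the protocol cites reliability only, which is why the standard mapping stays alongside it, and an imprecise heroin estimate.
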